### **7.8. Treatment after the End of the Study**

Not applicable. Tirzepatide will not be made available to subjects after completion of the study.

## 8. Discontinuation Criteria

Subjects discontinuing from the study prematurely for any reason should complete the ET visit and safety follow-up visit procedures per Section 2 of this protocol.

### 8.1. Discontinuation from Study Treatment

#### 8.1.1. Permanent Discontinuation from Study Treatment

Possible reasons leading to permanent discontinuation of IP:

- The subject requests to discontinue IP
- If a subject is inadvertently enrolled and it is determined that continued treatment with IP would not be medically appropriate (Section 8.1.3 Discontinuation of Inadvertently Enrolled Subjects)
- If a subject is diagnosed with acute or chronic pancreatitis after randomization
- If a subject is diagnosed with MTC after randomization
- If a subject is diagnosed with an active or untreated malignancy (other than basal or squamous cell skin cancer, in situ carcinomas of the cervix, or in situ prostate cancer) after randomization
- If a subject is diagnosed with a significant IP-related hypersensitivity reaction
- If a subject is diagnosed with any other TEAE, SAE, or clinically significant laboratory value for which the investigator believes that permanent IP discontinuation is the appropriate measure to be taken
- If female subject becomes pregnant

Discontinuation of the IP for abnormal liver tests **should be considered** by the investigator when a subject meets 1 of the following conditions after consultation with the Lilly designated medical monitor:

- ALT or AST >8X ULN for healthy subjects
- ALT or AST >5X ULN for more than 2 weeks or
- ALT or AST >3X ULN and TBL >2X ULN or international normalized ratio >1.5 or
- ALT or AST >3X ULN the appearance of fatigue, nausea, vomiting, right upper quadrant pain or tenderness, fever, rash, and/or eosinophilia (>5%)
- Alkaline phosphatase (ALP) >3X ULN
- ALP >2.5X ULN and TBL >2X ULN
- ALP >2.5 ULN with the appearance of fatigue, nausea, vomiting, right quadrant pain or tenderness, fever, rash, and/or eosinophilia (>5%).

- Drug-related vomiting requiring intravenous (IV) hydration treatment or causing severe distress (prevents daily activities and results in no appetite, or requires an emergency department visit, or hospitalization), that cannot be resolved by temporary interruption of IP (Section 8.1.2 Temporary Interruption of IP).

Subjects who discontinue IP early will be also discontinued from the study after performing the ET visit and safety follow-up visit procedures, as specified in Section 2 (Schedule of Activities).

### ***8.1.2. Temporary Interruption of Investigational Product***

In certain situations after randomization, for example, if GI tolerability AEs occur, the investigator may need to temporarily interrupt IP. Temporary interruptions are allowed during the dose escalation period (ie, while the dose is lower than 15 mg) and not during the maintenance phase of dosing with 15 mg. Investigators should immediately inform the sponsor, that IP has been temporarily interrupted. During an event that requires temporary interruption of study treatment, only 1 dose may be skipped. Every effort should be made by the investigator to maintain subjects on IP and to restart IP after temporary interruption, as soon as it is assessed as safe to do so. The subject should resume study treatment administration at the scheduled dose level, per protocol. If 2 or more episodes of study interruptions occur in the same subject, these cases will be reviewed by the investigator (or his/her designee) and Lilly to assess the feasibility of the subject's further participation in the study. If IP interruption is due to an AE, the event will be documented and followed according to the procedures in Section 9.2 (Adverse Events). The data related to temporary interruption of study treatment will be documented in source documents and entered into the eCRF.

### ***8.1.3. Discontinuation of Inadvertently Enrolled Subjects***

If the sponsor or investigator identifies a subject who did not meet enrollment criteria and was inadvertently enrolled, a discussion must occur between the Lilly CP/CRP and the investigator to determine if the subject may continue in the study. If both agree it is medically appropriate to continue, the investigator must obtain documented approval from the Lilly CP/CRP to allow the inadvertently enrolled subject to continue in the study with or without continued treatment with IP.

## **8.2. Discontinuation from the Study**

In addition to the situations that result in IP discontinuation described in Section 8.1.1 (Permanent Discontinuation from Study Treatment), subjects will be discontinued from the study in the following circumstances:

- Enrollment in any other clinical study involving an IP or enrollment in any other type of medical research judged not to be scientifically or medically compatible with this study
- Participation in the study needs to be stopped for medical, safety, regulatory, or other reasons consistent with applicable laws, regulations, and Good Clinical Practice
- Investigator Decision

- the investigator decides that the subject should be discontinued from the study
- if the subject, for any reason, requires treatment with another therapeutic agent that has been demonstrated to be effective for treatment of the study indication, discontinuation from the study occurs prior to introduction of the new agent
- Subject Decision
  - the subject, or legal representative, requests to be withdrawn from the study.

### **8.3. Subjects Lost to Follow-up**

A subject will be considered lost to follow-up if he or she repeatedly fails to return for scheduled visits and is unable to be contacted by the study site. Site personnel are expected to make diligent attempts to contact subjects who fail to return for a scheduled visit or were otherwise unable to be followed up by the site.

## 9. Study Assessments and Procedures

Section 2 lists the Schedule of Activities, detailing the study procedures and their timing (including tolerance limits for timing).

[Appendix 2](#) lists the laboratory tests that will be performed for this study.

[Appendix 5](#) provides a summary of the approximate number and volume of invasive samples, for all sampling, during the study.

The specifications in this protocol for the timings of safety and sample collections are given as targets to be achieved within reasonable limits. Modifications may be made to the time points based upon emerging clinical information. The scheduled time points may be subject to minor alterations; however, the actual time must be recorded correctly in the eCRF. Failure or delays (ie, outside stipulated time allowances) in performing procedures or obtaining samples due to legitimate clinical issues (eg, equipment technical problems, venous access difficulty, or subject defaulting or turning up late on an agreed scheduled procedure) will not be considered as protocol deviations but the CRU will still be required to notify the sponsor in writing via a file note.

Unless otherwise stated in subsections below, all samples collected for specified laboratory tests will be destroyed within 60 days of receipt of confirmed test results. Certain samples may be retained for a longer period, if necessary, to comply with applicable laws, regulations, or laboratory certification standards.

### 9.1. Efficacy Assessments

In this study, the measures used to assess mechanisms of action of study treatments with respect to energy balance, lipid and carbohydrate metabolism, and insulin sensitivity are considered efficacy measures. The planned assessments will be performed at baseline and at the end of the treatment period at 18 weeks ( $\pm 1$  week).

All parameter calculations, when applicable, and analyses are described in Section [10.3](#) (Statistical Analyses) or in the statistical analysis plan (SAP).

#### 9.1.1. Primary Efficacy Assessment and Procedure

The primary efficacy measure in the study is the change from baseline to Week 18 (Visit 20) in SMR for comparison of tirzepatide with placebo. The change in SMR will be measured in the respiratory chamber (whole-room calorimetry).

The SMR extrapolated to 24 hours will be calculated:

- SMR = average SMR\*1440, where average SMR is the average minute by minute EE for the sleep time period.

### **9.1.2. Secondary Efficacy Assessments and Procedures**

The change from baseline to Week 18 (Visit 20) for the following secondary efficacy measures will be used for secondary objectives to compare tirzepatide with placebo.

Secondary efficacy measure to assess the effect of study treatment on appetite, measured by visual analog scale (VAS), and food intake:

- appetite (VAS) for hunger, fullness, satiety, prospective food consumption, desire for specific foods, and the overall appetite score, assessed at fasting and during standardized mixed-meal tolerance test (sMMTT) (van Can et al. 2014; Flint et al. 2000; Flint et al. 2013);
- food intake assessed by ad libitum meal test (see [Appendix 6](#), Section 6.5 for description of parameters);

Secondary efficacy measure to assess the effect of study treatment on EE:

- 24-hour EE, defined as the total EE for the 23-hour measurement period in the respiratory chamber extrapolated to 24 hours;  
$$\text{EE} = 3.941 * \text{total oxygen consumption } [\text{VO}_2] + 1.106 * \text{total carbon dioxide production } [\text{VCO}_2] - 2.17 * [\text{urinary nitrogen}] \text{ (Weir JB deV 1949);}$$

Secondary efficacy measure to assess the effect of study treatment on substrate oxidation rates:

- 24-hour respiratory quotient (RQ), defined as the ratio of VCO2 to VO2 during the 23-hour measurement period in the respiratory chamber and extrapolated to 24 hours;  
$$\text{RQ} = \text{VCO}_2 / \text{VO}_2;$$
- sleep RQ, defined as the ratio of VCO2 to VO2 during sleep time points;
- RQ<0.80, defined as the cut point for high lipid oxidation of RQ; lipid oxidation will be calculated and corrected for protein oxidation; the total number of minutes with RQ <0.80, termed “lipid oxidation duration,” during each 23-hour measurement period will be recorded; protein oxidation will be determined from urine nitrogen that will be collected during 2 periods for each calorimeter day;

- substrate oxidation for fat, protein, and carbohydrates (Frayn 1983; Jéquier et al. 1987);

Protein Oxidation =  $6.25 * [\text{urinary nitrogen}]$

Fat Oxidation =  $1.689 * [\text{VO}_2] - 1.689 * [\text{VCO}_2] - 0.324 * [\text{protein oxidation}]$

Carbohydrate Oxidation =  $4.113 * [\text{VCO}_2] - 2.907 * [\text{VO}_2] - 0.375 * [\text{protein oxidation}]$

Secondary efficacy measure to assess the effect of study treatment on BW and body composition:

- BW (kg)
- body fat-free mass (kg) measured by the difference between BW and body fat mass
- body fat mass (kg) measured using DXA
- Percentage of body fat mass measured using DXA

Secondary efficacy measure to assess the effect of study treatment on lipid metabolism:

- triglycerides, cholesterol, low-density lipoprotein (LDL), very low-density lipoprotein (VLDL), and HDL cholesterol, free fatty acid (FFA), glycerol, 3-hydroxybutyrate, and acylcarnitines assessed during sMMTT;
- apolipoprotein B-48 (ApoB-48), apolipoprotein B-100 (ApoB-100), apolipoprotein C-III (ApoC-III), and lipoprotein lipase (LPL) during sMMTT.
- leptin, adiponectin, insulin-like growth factor binding protein (IGFBP) 1 and 2 at fasting

Secondary efficacy measure to assess the effect of study treatment on insulin sensitivity:

- fasting insulin resistance as measured by the HOMA2 method (HOMA2-IR) (Hill et al. 2013) and postprandial insulin sensitivity indices (Matsuda [Matsuda and DeFronzo 1999], Oral Glucose Insulin Sensitivity [OGIS] Index [Mari et al. 2001], and Stumvoll Index [Stumvoll et al. 2000]); assessed during sMMTT (Hill et al. 2013);

Secondary efficacy measure to assess the effect of study treatment on glucose control:

- fasting and postmeal glucose (total and incremental area under the concentration versus time curve (AUC) from time zero to 240 minutes after start of the meal [ $\text{AUC}_{0-240\text{min}}$ ]) during sMMTT;
- hemoglobin A1c

### **9.1.3. Exploratory Efficacy Assessments and Procedures**

The change from baseline to Week 18 (Visit 20) for following exploratory efficacy measures will be used for exploratory objectives to compare tirzepatide with placebo.

Exploratory efficacy measure to assess the effect of study treatment on GIPR signaling, lipid metabolism, carbohydrate metabolism, and insulin signaling pathways in SC adipose tissue:

- markers of GIPR signaling, lipid metabolism, carbohydrate metabolism, and insulin signaling pathways as measured in exploratory messenger ribonucleic acid (mRNA) expression, lipidomics, metabolomics, or targeted protein assays of SC adipose tissue biopsy samples, receptor expression, signal transduction, and metabolic changes in adipose tissue.

## 9.2. Adverse Events

Investigators are responsible for monitoring the safety of subjects who have entered this study and for alerting Lilly or its designee to any event that seems unusual, even if this event may be considered an unanticipated benefit to the subject.

The investigator is responsible for the appropriate medical care of subjects during the study.

Investigators must document their review of each laboratory safety report.

The investigator remains responsible for following, through an appropriate health care option, AEs that are serious or otherwise medically important, considered related to the IP or the study, or that caused the subject to discontinue the IP before completing the study. The subject should be followed until the event resolves, stabilizes with appropriate diagnostic evaluation, or is reasonably explained. The frequency of follow-up evaluations of the AE is left to the discretion of the investigator.

The investigator will record all AE/SAE information in the eCRF. After the ICF is signed, study site personnel will record, via eCRF, the occurrence and nature of each subject's preexisting conditions, including clinically significant signs and symptoms of the disease under treatment in the study. Additionally, site personnel will record any change in the condition(s) and the occurrence and nature of any AEs.

The investigator will interpret and document whether or not an AE has a reasonable possibility of being related to study treatment, study device, or a study procedure, taking into account the disease, concomitant treatment or pathologies.

A "reasonable possibility" means that there is a potential cause and effect relationship between the IP, study device and/or study procedure and the AE.

Planned surgeries should not be reported as AEs unless the underlying medical condition has worsened during the course of the study.

If a subject's IP is discontinued as a result of an AE, study site personnel must report this to Lilly or its designee via eCRF.

### **9.2.1. Serious Adverse Events**

An SAE is any AE from this study that results in one of the following:

- death
- initial or prolonged inpatient hospitalization
- a life-threatening experience (that is, immediate risk of dying)
- persistent or significant disability/incapacity
- congenital anomaly/birth defect
- important medical events that may not be immediately life-threatening or result in death or hospitalization but may jeopardize the subject or may require intervention to prevent one of the other outcomes listed in the definition above.

Study site personnel must alert the Lilly CRP/CP, or its designee, of any SAE as soon as practically possible.

Additionally, study site personnel must alert Lilly Global Patient Safety, or its designee, of any SAE within 24 hours of investigator awareness of the event via a sponsor-approved method. If alerts are issued via telephone, they are to be immediately followed with official notification on study-specific SAE forms. This 24-hour notification requirement refers to the initial SAE information and all follow-up SAE information.

Although all AEs are recorded in the eCRF after signing informed consent, SAE reporting to the sponsor begins after the subject has signed informed consent and has received IP. However, if an SAE occurs after signing informed consent, but prior to receiving IP, AND is considered reasonably possibly related to a study procedure then it MUST be reported.

Investigators are not obligated to actively seek AEs or SAEs in subjects once they have discontinued from and/or completed the study (the subject summary eCRF has been completed). However, if the investigator learns of any SAE, including a death, at any time after a subject has been discharged from the study, and he/she considers the event reasonably possibly related to the study treatment or study participation, the investigator must promptly notify Lilly.

Pregnancy (maternal or paternal exposure to IP) does not meet the definition of an AE. However, to fulfill regulatory requirements any pregnancy should be reported following the SAE process to collect data on the outcome for both mother and fetus.

#### **9.2.1.1. Suspected Unexpected Serious Adverse Reactions**

Suspected unexpected serious adverse reactions (SUSARs) are serious events that are not listed in the IB and that the investigator reports as related to IP or procedure. Lilly has procedures that will be followed for the recording and expedited reporting of SUSARs that are consistent with global regulations and the associated detailed guidances.

## 9.2.2. Adverse Events of Special Interest

### 9.2.2.1. Hypoglycemia

Subjects will be trained during Visit 2 about signs and symptoms of hypoglycemia and how to treat hypoglycemia.

Investigators should use the following definitions and criteria when diagnosing and categorizing an episode considered to be related to hypoglycemia (the PG values in this section refer to values determined by a laboratory or International Federation of Clinical Chemistry and Laboratory Medicine plasma-equivalent glucose meters and strips) (American Diabetes Association 2017):

#### *Glucose Alert Value (Level 1):*

- **Documented symptomatic hypoglycemia** is defined as any time a subject feels that he or she is experiencing symptoms and/or signs associated with hypoglycemia, and has a PG level of  $\leq 70$  mg/dL ( $\leq 3.9$  mmol/L).
- **Documented asymptomatic hypoglycemia** is defined as any event not accompanied by typical symptoms of hypoglycemia, but with a measured PG  $\leq 70$  mg/dL ( $\leq 3.9$  mmol/L).
- **Documented unspecified hypoglycemia** is defined as any event with no information about symptoms of hypoglycemia available, but with a measured PG  $\leq 70$  mg/dL ( $\leq 3.9$  mmol/L).

#### *Clinically Significant Hypoglycemia (Level 2):*

- **Documented symptomatic hypoglycemia** is defined as any time a subject feels that he/she is experiencing symptoms and/or signs associated with hypoglycemia, and has a PG level of  $< 54$  mg/dL ( $< 3.0$  mmol/L).
- **Documented asymptomatic hypoglycemia** is defined as any event not accompanied by typical symptoms of hypoglycemia, but with a measured PG  $< 54$  mg/dL ( $< 3.0$  mmol/L).
- **Documented unspecified hypoglycemia** is defined as any event with no information about symptoms of hypoglycemia available, but with a measured PG  $< 54$  mg/dL ( $< 3.0$  mmol/L).

#### *Severe Hypoglycemia (Level 3):*

- **Severe hypoglycemia** is defined as an episode with severe cognitive impairment requiring the assistance of another person to actively administer carbohydrate, glucagon, or other resuscitative actions. These episodes may be associated with sufficient neuroglycopenia to induce seizure or coma. Blood glucose measurements may not be available during such an event, but neurological recovery attributable to the restoration of BG to normal is considered sufficient evidence that the event was induced by a low BG concentration.

***Other Hypoglycemia Categories:***

- **Nocturnal hypoglycemia** is defined as any hypoglycemic event that occurs between bedtime and waking.

If a hypoglycemic event meets the criteria of severe, it needs to be recorded as serious on the AE eCRF and reported to Lilly as an SAE.

To avoid duplicate reporting, all consecutive PG values  $\leq 70$  mg/dL (3.9 mmol/L) occurring within a 1-hour period may be considered to be a single hypoglycemic event (Weinberg et al. 2010; Danne et al. 2013).

In each case of suspected or confirmed hypoglycemia, it is important that the event be properly categorized, the effect of the intervention be assessed, and the frequency of hypoglycemia be evaluated. The role of dietary changes and physical exercise (or any other contributing factor) in the development of an event should be established. The subject should receive additional education, if deemed appropriate.

**9.2.2.2. Pancreatitis**

Acute pancreatitis is defined as an AE of interest in all studies with tirzepatide including this study. Acute pancreatitis is an acute inflammatory process of the pancreas that may also involve peripancreatic tissues and/or remote organ systems (Banks and Freeman 2006). The diagnosis of acute pancreatitis requires 2 of the following 3 features:

- abdominal pain, characteristic of acute pancreatitis (generally located in the epigastrium and radiates to the back in approximately half the cases [Banks and Freeman 2006; Koizumi et al. 2006]; the pain is often associated with nausea and vomiting);
- serum amylase (total and/or pancreatic) and/or lipase  $\geq 3X$  ULN
- characteristic findings of acute pancreatitis on computed tomography (CT) scan or magnetic resonance imaging (MRI).

If acute pancreatitis is suspected, appropriate laboratory tests (including levels of pancreatic amylase and lipase) should be obtained via the local laboratory. Imaging studies, such as abdominal CT scan with or without contrast, MRI, or gallbladder ultrasound, should be performed. If laboratory values and/or abdominal imaging support the diagnosis of acute pancreatitis, the subject must discontinue IP, and will be discontinued from the study after completing all ET and follow-up procedures. A review of the subject's medical data, including concomitant medications, should be conducted to assess potential causes of pancreatitis.

Each case of AE of pancreatitis must be reported. If typical signs and/or symptoms of pancreatitis are present and confirmed by laboratory values (lipase or amylase [total and/or pancreatic]) and imaging studies, the event must be reported as an SAE. For a potential case that does not meet all of these criteria, it is up to the investigator to determine the seriousness of the case (AE or SAE) and the relatedness of the event to IP.

Each subject will have measurements of amylase and lipase, part of safety laboratory tests as shown in Section 2 (Schedule of Activities) to assess the effects of study treatment on pancreatic enzyme levels. Serial measures of pancreatic enzymes have limited clinical value for predicting episodes of acute pancreatitis in asymptomatic subjects (Nauck et al. 2017; Steinberg et al. 2017a; Steinberg et al. 2017b). Thus, further diagnostic follow-up of cases of asymptomatic pancreatic hyperenzymemia (lipase and/or pancreatic amylase  $\geq 3$ X ULN) is not mandated but may be performed based on the investigator's clinical judgment and assessment of the subject's overall clinical condition. If further diagnostic assessment due to asymptomatic hyperenzymemia will be warranted, it should follow Lilly standard algorithm for the monitoring of pancreatic enzymes (refer to [Appendix 7](#)).

All suspected cases of acute or chronic pancreatitis will be adjudicated by an independent clinical endpoint committee. In addition, all cases of pancreatic hyperenzymemia that undergo additional diagnostic follow-up, as well as the AEs of severe or serious abdominal pain of unknown etiology will also be submitted to the adjudication committee to assess for possible pancreatitis or other pancreatic disease. Relevant data from subjects with possible, probable, or definite acute or chronic pancreatitis and those with severe or serious abdominal pain will be entered into a specifically designed eCRF page by study site or Lilly staff. The adjudication committee representative will enter the results of adjudication in a corresponding eCRF page.

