## Pancreatic Enzymes: Safety Monitoring Algorithm for Subjects/Patients without Symptoms of Pancreatitis

Follow this algorithm when the value(s) for serum lipase and/or amylase are  $\geq 3$ X ULN.

1. Symptomatic – related primarily to abdominal pain consistent with pancreatitis; however, severe nausea, vomiting and other symptoms may be considered by the investigator as symptomatic as well.

2. If, at any time, in the opinion of the investigator, patient/subject has symptoms of acute pancreatitis irrespective of L/A results:

- (a) Consult appropriate specialist for assessment and management
- (b) Assess for causes of pancreatitis
- (c) Stop study drug
- (d) Notify Lilly

3. L/A = Lipase and/or amylase. Either or both enzymes can be measured and either or both can be used to meet the algorithm criteria.

4. Abdominal imaging is most valuable when performed at the time of elevated enzyme values. If in the opinion of the radiologist or investigator, it is safe for the patient/subject to receive contrast, an enhanced abdominal CT is preferred. MRI is also an acceptable imaging modality.

5. As minimum, test hepatic analytes, triglycerides, and calcium, and record all concomitant medications

6. Imaging results positive or negative for signs of acute pancreatitis

Abbreviations: CT = computed tomography; L/A = lipase and/or amylase MRI = magnetic resonance imaging; ULN = upper limit of normal.

Subjects diagnosed with pancreatitis will be discontinued from the study. Investigators will be responsible for following, through an appropriate healthcare option, these pancreatitis AEs until the events resolve or are explained. Adverse events that meet the diagnostic criteria of acute pancreatitis will be captured as serious adverse events (SAEs). For all other pancreatic AEs (such as idiopathic or asymptomatic pancreatic enzyme abnormalities), the investigator will be responsible for determining the seriousness of the event (AE or SAE) and the relatedness of the event to investigational product.

---

**Appendix 8. Protocol Amendment I8F-MC-GPGU(f)  
Summary - A Randomized, Placebo-Controlled, Parallel-  
Arm Study to Investigate the Effect of Once-Weekly  
Tirzepatide on Energy Expenditure and Food Intake in  
Obese Subjects**

---

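### Protocol Section 9.2.2.2 lets the investigator classify some diagnosed acute pancreatitis as non-serious, while the closing text of Appendix 7 requires an SAE

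*Protocol*

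**What the plan says.** Protocol Section 9.2.2.2 sets the diagnosis first: "The diagnosis of acute pancreatitis requires 2 of the following 3 features". The features are characteristic abdominal pain, serum amylase and/or lipase at or above 3X ULN, and characteristic CT or MRI findings.

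The same section then gives the reporting rule. "If typical signs and/or symptoms of pancreatitis are present and confirmed by laboratory values" (lipase or amylase) "and imaging studies, the event must be reported as an SAE". A potential case that "does not meet all of these criteria, it is up to the investigator to determine the seriousness of the case", and its relatedness to study drug.

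Appendix 7 (Pancreatic Monitoring) ends with a paragraph on subjects diagnosed with pancreatitis. It says: "Adverse events that meet the diagnostic criteria of acute pancreatitis will be captured as serious adverse events (SAEs"). It continues: "For all other pancreatic AEs (such as idiopathic or asymptomatic pancreatic enzyme abnormalities), the investigator will be responsible" for deciding seriousness and relatedness.

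Section 9.2.1 gives the general SAE definition, which includes "important medical events that may not be immediately life-threatening or result in death or hospitalization but may jeopardize the subject". It also requires the site to alert the sponsor's safety group "of any SAE within 24 hours of investigator awareness of the event". SAP Section 6.10.3 lists subjects with SAEs. SAP Section 6.10.5.2 separately lists investigator-reported and adjudicated pancreatitis and treats adjudication-confirmed treatment-emergent cases as AESIs.

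**The concern.** The diagnosis needs two features. The mandatory SAE rule in Section 9.2.2.2 needs signs or symptoms, laboratory confirmation and imaging confirmation together. The Appendix 7 rule needs only that the diagnosis is met. A subject can therefore have acute pancreatitis by the protocol's own definition and be left to investigator judgment in one place and be a required SAE in another.

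The mismatch also shows inside Section 9.2.2.2. Study drug must stop when laboratory values, imaging or both support the diagnosis, whereas the SAE sentence requires both. A subject can be withdrawn for pancreatitis while that section still permits a non-serious classification.

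Pancreatitis is a named event of interest. For an affected case, the page the site follows decides whether the 24-hour report is due and whether the subject enters the SAE listing.

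**Working it through.** No arithmetic applies. The check applies both rules to the same hypothetical cases.

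**Inputs**
- Diagnosis (Section 9.2.2.2): at least 2 of pain, enzymes at or above 3X ULN, and CT/MRI findings.
- Rule A (Section 9.2.2.2): a mandatory SAE requires typical signs and/or symptoms, confirming laboratory values and confirming imaging. Otherwise the investigator decides.
- Rule B (closing text of Appendix 7): a mandatory SAE requires only that the diagnostic criteria are met. Otherwise the investigator decides.

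Rule B does not restate the criteria. The Appendix 7 flow chart is not reproduced in the text I worked from. In the readable text, the only criteria are the 2-of-3 features.

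Rule A's terms are looser than the diagnostic features. Its laboratory term carries no 3X ULN threshold. Its imaging term is not limited to CT or MRI, and the same section names gallbladder ultrasound among the imaging studies. Its first term is typical signs and/or symptoms, which is wider than characteristic pain.

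| Case | Diagnosed? | Rule A | Rule B | Result |
|---|---|---|---|---|
| Pain, enzymes ≥3X ULN, CT/MRI findings | Yes | SAE | SAE | Agree |
| Pain, lipase ≥3X ULN, imaging negative | Yes | Investigator decides | SAE | Conflict |
| Pain, lipase ≥3X ULN, no CT/MRI findings, ultrasound judged confirmatory | Yes | Can be SAE | SAE | Can agree |
| Pain, CT/MRI findings, enzymes normal | Yes | Investigator decides | SAE | Conflict |
| Pain, CT/MRI findings, enzymes raised below 3X ULN and judged confirmatory | Yes | Can be SAE | SAE | Can agree |
| Enzymes ≥3X ULN, CT/MRI findings, no characteristic pain | Yes | SAE if another typical sign or symptom is present; otherwise investigator decides | SAE | Depends |
| Fewer than two features | No | Investigator decides, unless Rule A's looser terms are all met | Investigator decides | Normally agree |

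The clear conflict is a diagnosed case with no confirmatory laboratory value at all, or no confirmatory imaging at all.

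**What the conflict can change.** If the case meets any Section 9.2.1 criterion, it is an SAE under either rule. If it meets none, Rule A permits a non-serious classification and Rule B does not. Three things then follow the choice: the SAE label, the 24-hour report, and appearance in the SAE listing.

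**What it cannot change.** Independent adjudication covers all suspected cases (Section 9.2.2.2). The pancreatitis listing and AESI status do not depend on seriousness (SAP Section 6.10.5.2). A pancreatitis diagnosis ends study drug and participation (Sections 8.1.1 and 9.2.2.2). Footnote 2 of Appendix 7 tells the site to stop drug and notify the sponsor whenever the investigator judges that symptoms of acute pancreatitis are present, whatever the enzyme result. No efficacy endpoint, sample size or error rate is involved.

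**The case against.** The strongest reply is that the two texts need not meet. Section 9.2.2.2 gives discretion over a potential case, and a diagnosed case is arguably no longer only potential. Appendix 7's algorithm is headed for subjects without symptoms, and Section 9.2.2.2 sends readers there for asymptomatic enzyme elevation.

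Neither reading settles the matter. If potential excludes diagnosed cases, a diagnosed case lacking laboratory or imaging confirmation falls under no reporting rule in Section 9.2.2.2, which still differs from Appendix 7. The closing paragraph of Appendix 7 is worded for any subject diagnosed with pancreatitis. It cites asymptomatic enzyme abnormalities as an example of the other events, so its SAE sentence is not confined to asymptomatic subjects. The unseen flow chart is a genuine reservation about whether further criteria appear there.

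Three parts of the opposing case stand in full:
- A site that reports every diagnosed case as an SAE satisfies both texts.
- The important-medical-event criterion in Section 9.2.1 may already capture many such cases, although it is a judgment.
- Footnote 2 means the sponsor is told of symptomatic cases individually. It gives no time limit, however, and neither adjudication nor the periodic sponsor review in Section 9.4.5 is said to assign seriousness or set the 24-hour report.

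A reader might infer that the rules conflict for every case with exactly two features, or count the feature combinations that conflict. The documents do not support this. The SAE sentence in Section 9.2.2.2 sets no enzyme threshold, does not restrict imaging to CT or MRI, and accepts signs or symptoms other than characteristic pain. Some two-feature cases are therefore already mandatory SAEs there.

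**Conclusion.** The inconsistency is real and minor. For a diagnosed case without any confirmatory laboratory value, or without any confirmatory imaging, Section 9.2.2.2 allows a non-serious classification that the closing text of Appendix 7 does not. Both texts are current protocol wording.

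The effect is confined to diagnosed cases not already serious under Section 9.2.1. The documents give no pancreatitis rate, so no expected number of affected cases is claimed in a trial of up to 56 randomized subjects. A reader might also infer that pancreatitis could escape safety oversight. The documents do not support that, given adjudication, the dedicated listing, AESI status, discontinuation and the footnote 2 notice for symptomatic subjects.

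The conclusion assumes that the diagnostic criteria meant in Appendix 7 are the 2-of-3 features in Section 9.2.2.2.

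**What to change.** In Section 9.2.2.2, replace the two reporting sentences with a rule that any case meeting the 2-of-3 diagnostic criteria must be reported as an SAE, and that the investigator determines seriousness only for cases that do not meet them. In Appendix 7, add a cross-reference to those criteria. Aligning towards Appendix 7 is the more protective of the two directions.

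Before database lock, compare every pancreatitis event recorded as non-serious with the 2-of-3 criteria, using the dedicated pancreatitis eCRF page, and query any that meet them.

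The cost is a minor amendment or a written clarification to the single site, plus one data check. No new data are needed.
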